Specific hypotheses: *Hypotheses 1.1 and 2.1 (neuropsychiatric outcomes)*. Following DAA therapy and obtaining a sustained viral response (SVR), 1.1: participants will show improved neuropsychiatric outcomes (e.g., cognitive function, fatigue, mood), as compared to baseline (pre-DAA therapy). 2.1: participants without AUDs will show greater improvement in neuropsychiatric outcomes than participants with AUDs. *Hypothesis 1.2 and 2.2 (neuroimaging outcomes)*. Reduced fractional anisotropy (FA) will be observed in the tracts that connect regions between which there is decreased functional connectivity. 1.2 and 2.2: Disintegrity within white matter tracks [as measured by FA and mean diffusivity (MD)] observed at baseline visits will be improved following DAA therapy, with greater improvement observed in participants without AUDs. On the fMRI Balloon analogue risk task (BART) and Monetary incentive delay task (MID), adults with HCV will be significantly more likely to display more impulsivity during the baseline visit, as compared to the post-DAA therapy visit. It is hypothesized that AUD may attenuate the positive antiviral therapy effects on impulsivity. *Hypothesis 1.3 and 2.3 (immune activation profile)*. Inflammatory profiles will be associated with neuropsychiatric impairments and alterations in white matter integrity and cortical activity. Following DAA therapy and obtaining an SVR, 1.3: participants will show reduced immune activation profiles (i.e., restored T cell phenotypes and a reduced inflammatory profile), as compared to baseline, and 2.3: participants without AUDs will show greater a reduction in inflammatory factors than participants with AUDs.

Scientific Rationale and Significance

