potential interaction of these factors—after possibly controlling for other subject-level covariates that remain constant (or nearly so) over the six months (e.g., age, sex, HCV genotype). Variables that could meaningfully vary over time (e.g., TFLB score, CIWA-Ar score) will be summarized in terms of a difference and then included as a covariate. Number of DAA therapy provider contacts will be included as an extra covariate that counts total contacts. All models will use “robust” (sandwich estimators) of variance to guard against potential misspecification of the underlying distribution of change scores or due to non-constant variance among the groups (Long and Ervin, 2000). The AUD \times HCV interaction will be assessed first in all models fit, and will be removed from the model only if evidence suggests ($p > 0.10$) these two factors don’t modify one another; otherwise, subsequent comparisons of each separate effect will be made within each level of the other (e.g., effect of HCV separately characterized for those with and then without AUD).

A supervised and directed approach will be taken in the exploratory analysis of inflammatory biomarkers. Principal component analysis (PCA) will be used to reduce the collection of ~12 correlated immune factors to a smaller number of uncorrelated linear combinations (the principal components) of biomarkers [e.g., (Bowman et al., 2012)]. Each component of this reduced set of uncorrelated patterns of inflammatory expression will be subjected to the same general linear models described earlier to determine whether AUD, HCV or AUD \times HCV are associated with it, even after adjustment for other covariates. If the overall test of association in the linear model shows significant ($p < 0.10$, for initial screen) variation among the groups, then separate models will be conducted on those biomarkers that most heavily contribute/dominate the principal component being screened. In this way, we may identify combinations of markers that are sensitive to AUD and HCV treatment outcomes, particularly CNS function.

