Power. We estimated group size using fmripower (Mumford and Nichols, 2008). The MATLAB-based program calculates a power estimate given the between-group and within-subject error terms associated with a two tailed t-test of regression coefficients. The results suggested that 30 subjects (male and female) per group would yield a power of 0.8 for the test comparison. This sample size yields an 80% chance for us to identify AUD \times HCV interaction effects of 0.91 standard deviation (SD) or larger at the 0.10 level of significance. Use of the higher alpha-level is done to lessen the chance of making a type II (overlook) error and mistakenly omitting this term from the model. We also have 80% power for a 0.05-level test to detect any main effect, for either AUD or for HCV, of at least 0.51 SD in size. **Table 2** shows the smallest average change (between post- and pre-DAA therapy) among groups that would be of practical interest and the subsequent main effects (AUD+ vs AUD-; HCV+ vs HCV-) and interactions that derive from these minimally relevant average changes. The anticipated SD for the change scores was derived from reported SDs of each outcome supported by literature, and then converted to a SD for the difference assuming a modest correlation of 0.60 between pre- and post-DAA responses within the same subject. The principal comparisons proposed in this work parallel those in our preliminary work, and we were able to readily demonstrate differences in planned comparisons between the groups. Therefore, the proposed 30 subjects per group should provide us with sufficient power to test the predictions, anticipating that a small number of participants with HCV may not achieve SVR (n = ~3-6).

Table 2. Statistical power to evaluate antiviral therapy outcomes of significant clinical impact

Response/outcome	SD(diff)	Treatment group ^a			Effects and Power ^b			
		AUD-/HCV-	AUD-/HCV+	AUD+/HC V-	AUD+/HCV+	AUD main	HCV main	Interact.
Cognitive performance^c								
Attention	2.25	3.5	3.7	1.2	3.5	-1.25 (0.85)	1.25 (0.85)	2.1 (0.81)
Memory	2.50	3.0	3.4	0.4	3.0	-1.50 (0.91)	1.50 (0.91)	2.2 (0.78)
Executive function	1.80	2.0	2.1	0.3	2.0	-0.90 (0.78)	0.90 (0.78)	1.6 (0.78)
Behavioral response								
Impulsivity (BART/MID) ^d	1.35	0	-0.2	-0.1	-1.5	-0.70 (0.80)	-0.80 (0.90)	-1.20 (0.78)
Alcohol use (TLFB)	18.9	0	-1.0	-18	-36	-26.5 (0.99)	-9.50 (0.78)	-17.0 (0.79)
Mental health								
Depression (BDI)	4.0	0	-3.5	-2.7	-11.0	-5.1 (0.99)	-5.9 (0.99)	-4.8 (0.94)

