Fatigue (FSS)	0.63	0	-1.1	-0.8	-1.3	-0.5 (0.99)	-0.8 (0.99)	0.6 (0.83)
CNS microstructure^e								
FA	0.02	0	-0.001	-0.003	-0.02	-0.01 (0.91)	-0.01 (0.78)	-0.016 (0.78)
MD (x10 ⁵)	8.9	0	-6.0	7.5	15.0	14.5 (0.99)	0.75 (0.07)	13.5 (0.99)
Inflammatory profile								
Immune factor concentration ^f	4.05	0	-10	2.5	-3	4.75 (0.99)	-7.75 (0.99)	4.5 (0.92)
T cell subpopulations ^g	22.5 DP	0	-18 DP	0	-9 DP	4.5 (0.19)	-13.5 (0.90)	9 (0.29)
	27.0 DN	0	38 DN	0	19 DN	-9.5 (0.48)	28.5 (0.99)	-19 (0.61)

^aNumbers shown are minimally meaningful mean change scores, post- minus pre-DAA therapy, for the primary outcome variables. Conjectured standard deviation for a given outcome was based on published studies conducted by the PI and others, as referenced and converted to a standard deviation (SD) for the difference by conservatively assuming a correlation of 0.60 between post- and pre-DAA therapy values. ^bPower for main effects use 0.05 as level of significance while interaction uses 0.10. Based on n = 30 per group (N = 120 total). ^cNAB module scores are reported as demographically corrected standard index change scores. ^dHigher (i.e., less negative) values represent a stronger tendency to discount larger delayed rewards in favor of smaller immediate rewards. ^eNeuroimaging outcome projections are for brain regions and tracks most significantly affected by a history of HCV infection and alcohol abuse (e.g., insula, superior fronto-occipital fasciculus). ^fImmune factors included in the inflammatory profile: CRP, CXCL10, IL-1 β , IL-6, IL-8, IL-10, IL-18, MCP-1, MMP-3, S100B, TIMP-1, TNF- α . ^gT-cells will initially be evaluated for changes in the frequencies of double negative (DN; CD4-CD8-) and double positive (DP; CD4+CD8+) CD3+ cells; further investigation of subpopulations (e.g., effector, regulatory) will be conducted as described under Laboratory measures and in the Specific methods section.

Abbreviations: BDI = Beck Depression Inventory, 2nd Edition; CNS = central nervous system; DAA = direct acting antiviral therapy; BART/MID = Balloon analogue risk task/Monetary incentive delay task; FSS = Fatigue Severity Scale; FA = fractional anisotropy; MD = mean diffusivity; NAB = Neuropsychological Assessment Battery

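### The plan claims power for all its predictions, but Table 2 lists none for the AUD comparison among DAA-treated participants (Hypothesis 2.1), and its own cognitive means give that comparison 6–9%

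*Combined protocol and SAP*

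**What the plan says.** Under Specific hypotheses, the neuropsychiatric prediction is conditioned on having received DAA therapy and reached a sustained viral response (SVR). It then states "2.1: participants without AUDs will show greater improvement in neuropsychiatric outcomes than participants with AUDs". Hypotheses 1.2 and 2.2 say that white-matter abnormality "observed at baseline visits will be improved following DAA therapy, with greater improvement observed in participants without AUDs".

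Under Neuropsychiatric and laboratory measures, the AUD × HCV interaction is tested first and dropped if p > 0.10. If it is kept, "subsequent comparisons of each separate effect will be made within each level of the other".

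The Power paragraph gives 80% power for an interaction of 0.91 SD at the 0.10 level and, at the 0.05 level, 80% power "to detect any main effect, for either AUD or for HCV, of at least 0.51 SD in size". It says that Table 2 shows the smallest average changes of practical interest and "the subsequent main effects (AUD+ vs AUD-; HCV+ vs HCV-) and interactions that derive from these minimally relevant average changes". It ends with the statement that "the proposed 30 subjects per group should provide us with sufficient power to test the predictions", allowing for about 3–6 participants with HCV who may not reach SVR.

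Table 2 prints, for each outcome, the SD of the change score, a mean change for each of the four groups, and effect and power for AUD main, HCV main and interaction. Footnote a describes the group means as the smallest changes regarded as meaningful.

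**The concern.** HCV- participants receive no DAA therapy and cannot have an SVR, so Hypothesis 2.1 as written is an AUD comparison inside the HCV+ half of the study. Whenever the interaction is retained, the analysis rule leads to that same comparison. Table 2 has no column for it.

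A reader who meets the sufficiency sentence will naturally carry the cognitive AUD main-effect powers of 0.85, 0.91 and 0.78 over to the question of Aim 2: whether AUD limits cognitive gain in treated Veterans. If those powers do not apply to that question, a non-significant cognitive result would carry much less information than the plan suggests.

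**Working it through.** **Inputs.** From Table 2: SD of change 2.25 (attention), 2.50 (memory), 1.80 (executive), and the four group means. From footnote b: n = 30 per group, α = 0.05 for main effects and 0.10 for the interaction. Tests are two-sided, as in the Power paragraph. Assumed, because not stated: two-sided 0.05 for the treated pair, equal SD in all groups, no covariate adjustment, no drop-out. Power is from the noncentral t with 116 df.

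**Standard errors.** Main effect SD·√(2/60) = 0.183 SD; interaction SD·√(4/30) = 0.365 SD; treated pair SD·√(2/30) = 0.258 SD.

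**1. The plan's own figures.** Normal approximation: main (1.960 + 0.842) × 0.183 = 0.51 SD; interaction (1.645 + 0.842) × 0.365 = 0.91 SD. By t they are 0.516 and 0.913. Both agree with the plan. Cognitive AUD main-effect powers come out at 0.855, 0.903 and 0.775 (printed 0.85, 0.91, 0.78). Interaction powers come out at 0.815, 0.774 and 0.781 (printed 0.81, 0.78, 0.78). These are also the probabilities that the interaction is kept at Table 2's means.

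**2. The treated pair.** (1.960 + 0.842) × 0.258 = 0.72 SD; by t, 0.729 SD. Multiplying by the SDs gives 1.64, 1.82 and 1.31 points.

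**3. Power at Table 2's means.**

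| | AUD-/HCV+ | AUD+/HCV+ | Gap | Gap in SD | Power | Gap in HCV- pair | HCV- share of pooled AUD effect |
|---|---|---|---|---|---|---|---|
| Attention | 3.7 | 3.5 | 0.2 | 0.09 | 0.06 | 3.5 − 1.2 = 2.3 | 2.3/2.5 = 92% |
| Memory | 3.4 | 3.0 | 0.4 | 0.16 | 0.09 | 3.0 − 0.4 = 2.6 | 2.6/3.0 = 87% |
| Executive | 2.1 | 2.0 | 0.1 | 0.06 | 0.06 | 2.0 − 0.3 = 1.7 | 1.7/1.8 = 94% |

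The pooled AUD effect is the average of the two gaps, e.g. (2.3 + 0.2)/2 = 1.25 for attention.

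**4. The full two-step rule.** Simulating the rule (drop the interaction if p > 0.10 and use the pooled AUD test; otherwise test within HCV+) at Table 2's means gives a significant AUD result in the hypothesised direction with probability about 0.17, 0.23 and 0.18. Nearly all of this comes from the pooled test. The probability of dropping the interaction times the pooled power is 0.185 × 0.855 = 0.16, 0.226 × 0.903 = 0.20 and 0.219 × 0.775 = 0.17.

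**5. Restriction to SVR.** With 3 to 6 non-responders in total, split evenly, 28.5 to 27 per group remain and the detectable difference is 0.75–0.77 SD. With six lost in each HCV+ group (24 per group) it is about 0.82 SD. The plan does not say whether 3–6 is a total or per group.

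**6. Directions against the hypotheses.**
- Cognitive interaction: +2.1, +2.2, +1.6. Net of HCV- controls, the gain is 2.3, 2.6 and 1.7 with AUD, and 0.2, 0.4 and 0.1 without. Hypothesis 2.1 expects the reverse.
- Depression (BDI): −11.0 with AUD, −3.5 without. Improvement is larger with AUD.
- Fatigue (FSS): −1.3 with AUD, −1.1 without. Again larger with AUD; power for this 0.2-point gap is 0.23.
- FA: −0.001 and −0.02 in the two HCV+ groups, whereas Expected outcomes and alternative considerations looks for an increase.

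**The case against.** **Hypothesis 2.1 may be meant as the interaction.** The HCV- groups exist to separate the contribution of HCV and its cure, and whether AUD modifies the benefit of DAA therapy is an interaction question. Its cognitive power is printed as 0.78–0.81. This is a fair reading of the design, but it does not rescue the claim, because those powers are for an interaction of the opposite sign to the hypothesis.

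**The analysis would often use the pooled test.** A reader might infer that power for Hypothesis 2.1 is only about one half by applying the printed pooled effects (1.25, 1.50, 0.90) to 30 against 30. The documents do not support that. If the treated-pair effect equals the pooled effect, the interaction is zero, the rule drops it about 90% of the time, and the pooled test follows. Simulated power of the two-step rule is then 0.82, 0.87 and 0.75. This part of the objection stands, and the point does not rest on that scenario. It rests on Table 2's own means, where the interaction is kept with probability 0.77–0.82.

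**A target exists.** A reader might infer that the plan sets no target for the treated pair. It lists none, but footnote a gives both HCV+ means as meaningful changes, so 0.2, 0.4 and 0.1 points follow by subtraction.

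**Mood looks well powered.** The BDI gap in the treated pair is 7.5/4.0 = 1.9 SD, with power above 0.99. A reader might infer that mood is covered, but that power is for AUD+ improving more, which is not Hypothesis 2.1.

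**Covariates could sharpen the test.** For the largest cognitive gap (0.16 SD), reaching 80% power would need the residual SD cut by a factor of 0.729/0.16 = 4.6. That means covariates explaining 1 − 1/4.6² ≈ 95% of the variance.

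**The document is dated October 2024.** A revised power table is unlikely to change the design, and no passage says that a null result will be read as no AUD effect. Both are true, so the remedy concerns how power is stated and results are read.

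**Conclusion.** The sufficiency statement is not borne out for the cognitive part of Hypothesis 2.1. The treated-pair AUD contrast is detectable with 80% power at 0.73 SD, while Table 2's means imply 0.06–0.16 SD, with power 0.06–0.09 directly and about 0.17–0.23 under the full rule. No figure in Table 2 shows power for Hypothesis 2.1 in its stated direction on depression or fatigue either.

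This rests on two-sided 0.05 for the contrast, equal SDs, 30 per group with no losses, and Table 2's means taken at face value.

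The point goes no further than this. The cognitive powers contain no arithmetic error, and the 0.51 SD and 0.91 SD statements and Hypothesis 1.1 are unaffected. A reader might also infer direction conflicts in the MD and impulsivity rows. Those cannot be judged: the plan does not say which direction of MD is better, and footnote d describes delay discounting on a row labelled BART/MID.

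**What to change.** 1. Add the AUD contrast within HCV+ to Table 2, with its 80% detectable difference and the power at the stated cell means. The detectable difference is 0.73 SD; among SVR responders it is 0.75–0.77 SD if 3–6 is a total split evenly, and up to about 0.82 SD if six are lost per group. State which reading of 3–6 is intended.
2. Replace the sufficiency sentence with, for example:

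> With 30 per group there is 80% power for main effects of 0.51 SD (0.05 level), interactions of 0.91 SD (0.10 level) and an AUD difference among DAA-treated participants of 0.73 SD (0.05 level). Smaller cognitive and fatigue AUD differences in treated participants will be reported as estimates with 95% confidence intervals, and a non-significant result will not be read as no AUD effect.

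3. Reconcile the directions of the cognitive interaction, BDI, FSS and FA entries with Hypotheses 1.2, 2.1 and 2.2, and recompute power wherever a cell mean changes.

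The cost is recalculation and wording, with no added patients. The downside is a less favourable stated power for the AUD question in treated participants. If data are already collected, items 1 and 2 govern how the contrast is reported.

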Expected outcomes and alternative considerations. Results are expected to determine the extent of improvement in CNS function (including neuropsychiatric outcomes) that is gained by successful completion of DAA therapy and whether or not co-morbid AUDs affect HCV treatment outcomes. Our hypotheses would be supported by finding improved CNS function following successful completion of DAA therapy (*i.e.*, obtaining an SVR), including: i) increased FA in the tracts that previously connected regions between which there was decreased functional connectivity, ii) improved functional connectivity, iii) reduced impulsivity, and iv) improved cognitive abilities. Following DAA therapy, these changes in CNS function will be associated with reduced peripheral immune activation. Individuals with active AUDs and HCV may show attenuated benefits in CNS function and immune response, post-DAA therapy. In participants with HCV and co-morbid AUDs, cumulative disruptions in cerebral connectivity that result from anatomical disruptions may contribute to persistent cognitive deficits and elevated inflammatory profiles. Alternatively, it is possible that floor effects for some of the variables (e.g., BDI-II scores) may limit our ability to detect significant improvements. However, cognitive performance benefits have been reported following IFN-based therapy for HCV (Kraus et al., 2013, Kuhn et al., 2017), and we have observed improvements in depression and fatigue in patients who obtained SVR (Huckans et al., 2015). It is also possible that differences in the number of DAA therapy provider visits between participants in the HCV+ and HCV- groups may affect neuropsychiatric outcome variables (e.g., alcohol use behavior). To assess the impact of this potential confound, we plan to include that characteristic as an extra covariate. Because CNS recovery may continue beyond the SVR assessment timepoint, patients who agree to participate in the study will be asked to allow our research team permission (via the informed consent process) to contact them for future follow-up investigation, which is beyond the scope of this current protocol. We also considered the potential concern that there may be a lack of research participants with HCV (given the pace at which the VA is treating HCV); however, estimates indicate that by 2020, there will still be ~560,000 adults with HCV in the US (Chhatwal et al., 2016).

Table 3. Project timeline

Year 1	Year 2	Year 3	Year 4

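### For cognition, impulsivity and depression, Table 2's AUD × HCV interactions have AUD enlarging the net antiviral benefit, so their powers do not describe the attenuation the protocol predicts

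*Combined protocol and SAP*

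**What the plan says.** The direction of the AUD effect is stated in three places. Under Specific hypotheses, Hypothesis 2.1 says that after DAA therapy and SVR "participants without AUDs will show greater improvement in neuropsychiatric outcomes than participants with AUDs". The imaging hypotheses (1.2 and 2.2) add: "It is hypothesized that AUD may attenuate the positive antiviral therapy effects on impulsivity". Expected outcomes and alternative considerations repeats the idea: "Individuals with active AUDs and HCV may show attenuated benefits in CNS function and immune response, post-DAA therapy".

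The Power paragraph gives a detectable AUD × HCV interaction of 0.91 SD (80% power, 0.10 level) and a detectable main effect "of at least 0.51 SD in size" (0.05 level). It introduces Table 2 as showing the smallest average changes of practical interest, and ends by saying that "the proposed 30 subjects per group should provide us with sufficient power to test the predictions". Table 2 gives, for each outcome, an SD of the change score, a mean change in each of the four groups, and the resulting main effects, interaction and powers. Footnote a calls the cell values minimally meaningful changes.

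Under Statistical analyses and power, the interaction is the first term assessed in every model. It is dropped only if p > 0.10; otherwise each factor is compared within levels of the other.

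**The concern.** A power table supports a hypothesis when its assumed means have the shape of that hypothesis. If AUD attenuates the benefit of viral clearance, the HCV+ minus HCV- difference in change should be larger without AUD than with it. In five rows of Table 2 it is smaller without AUD.

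The interaction is the first term tested and the one that expresses attenuation relative to untreated controls. A significant interaction shaped like these rows would count against attenuation. A null result would be hard to interpret, because the size of attenuation the study could detect was never set against the size it expects. The statement that power is sufficient for the predictions therefore lacks support for these outcomes.

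**Working it through.** **Inputs.** Group means and SDs of change from Table 2; n = 30 per group; 0.10 level for the interaction and 0.05 for main effects (Table 2, footnote b). Sidedness is stated only for the fmripower step ("associated with a two tailed t-test of regression coefficients"). Two-sided 0.10 reproduces the printed powers, while one-sided 0.10 would give about 0.90 for attention against the printed 0.81.

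**Formulas.** Net benefit is HCV+ change minus HCV- change, within AUD level. Interaction I = (AUD+/HCV+ − AUD+/HCV-) − (AUD-/HCV+ − AUD-/HCV-). SE(I) = SD × √(4/30) = 0.365 SD. Power = Φ(|I|/SE − 1.645) + Φ(−|I|/SE − 1.645). Detectable interaction = (1.645 + 0.842) × 0.365 = 0.908 SD, matching the stated 0.91.

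**Step 1: reproduce Table 2.** For impulsivity and BDI a negative change is an improvement (for impulsivity, by footnote d).

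| Row | SD | HCV effect, AUD- | HCV effect, AUD+ | I | Printed power | Recomputed |
|---|---|---|---|---|---|---|
| Attention | 2.25 | 3.7 − 3.5 = 0.2 | 3.5 − 1.2 = 2.3 | 2.1 | 0.81 | 0.819 |
| Memory | 2.50 | 3.4 − 3.0 = 0.4 | 3.0 − 0.4 = 2.6 | 2.2 | 0.78 | 0.778 |
| Executive | 1.80 | 2.1 − 2.0 = 0.1 | 2.0 − 0.3 = 1.7 | 1.6 | 0.78 | 0.785 |
| Impulsivity | 1.35 | −0.2 − 0 = −0.2 | −1.5 + 0.1 = −1.4 | −1.2 | 0.78 | 0.785 |
| BDI | 4.0 | −3.5 − 0 = −3.5 | −11.0 + 2.7 = −8.3 | −4.8 | 0.94 | 0.950 |

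A noncentral t with 116 df gives 0.815, 0.774, 0.781, 0.781 and 0.948. The printed powers are sound, and in all five rows the net benefit is larger with AUD.

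**Step 2: raw change within the HCV+ groups (AUD- against AUD+).** BDI is −3.5 against −11.0, a gap of 7.5/4.0 = 1.88 SD favouring AUD+. Impulsivity is −0.2 against −1.5, or 1.3/1.35 = 0.96 SD favouring AUD+. Both conflict with the stated predictions on this reading too. Cognition does not: 3.7 against 3.5, 3.4 against 3.0, and 2.1 against 2.0 all favour AUD-. Those gaps are 0.2/2.25 = 0.09, 0.4/2.50 = 0.16 and 0.1/1.80 = 0.06 SD. With SE = SD × √(2/30) and a two-sided 0.05 level, power is 0.06, 0.09 and 0.06.

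**Step 3: source of the cognitive effects.** The AUD main effect averages the AUD difference in the two HCV strata. For attention, [(1.2 − 3.5) + (3.5 − 3.7)]/2 = (−2.3 − 0.2)/2 = −1.25. Memory is (−2.6 − 0.4)/2 = −1.50 and executive function (−1.7 − 0.1)/2 = −0.90. Nearly all of each main effect, and the whole size of the interaction, comes from the low AUD+/HCV- cell (1.2, 0.4, 0.3), a group that receives no DAA therapy.

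**Step 4: what attenuation would need.** An interaction of 0.91 SD is 0.91 × 2.25 = 2.05 points for attention, 2.28 for memory, 1.64 for executive function, 1.23 for impulsivity and 3.64 for BDI. The printed AUD- net benefits are 0.2, 0.4, 0.1, 0.2 and 3.5. With those cells held, even complete loss of benefit falls short in every row.

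**Step 5: illustration.** Assume the AUD- cells are kept and AUD cancels the benefit entirely. The interaction is then 0.09, 0.16, 0.06, 0.15 and 0.88 SD, and power at the 0.10 level is 0.11, 0.13, 0.10, 0.13 and 0.77.

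**Step 6: FA.** Both HCV+ cells are negative (−0.001 and −0.02), whereas Hypothesis 1.2 and Expected outcomes predict improvement, that is, rising FA. The interaction, (−0.02 + 0.003) − (−0.001) = −0.016, has AUD doing worse, which agrees with Hypothesis 2.2.

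**The case against.** Several objections have force.

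- **Sign does not affect two-sided power.** Correct: an attenuating interaction of the same size would have the same power. A reader might infer that the printed powers are wrong or that the trial is underpowered for any interaction. The documents support neither. What is missing is a scenario in which attenuation reaches that size.
- **Cognition agrees with Hypothesis 2.1 as worded.** Also correct. The hypothesis compares improvement with and without AUD after therapy, and the HCV+ cells and AUD main effects (printed powers 0.78 to 0.91) go that way. A reader might infer that a trial matching Table 2 would refute Hypothesis 2.1 across the board; for cognition it would not. But the HCV+ gaps are almost undetectable, and the main effects are driven by untreated participants.
- **The cells are minimally meaningful changes, not forecasts, and 0.91 SD is already stated.** True, but the paragraph uses these cells to claim power for the predictions, and a smallest effect of interest should still have the predicted shape. The fatigue row does: its net benefit is 1.1 without AUD and 0.5 with it.
- **Impulsivity is a weaker case.** Its prediction is hedged, sits under Hypotheses 1.2/2.2 rather than 2.1, and footnote d describes delay discounting while the row is BART/MID. The sign reading is therefore an assumption. On the opposite reading both HCV+ groups would become more impulsive after therapy, which also conflicts with the protocol.
- **Full cancellation is this review's assumption.** It is, and it is not an upper bound, since AUD+ participants could worsen.
- **Group size is attributed to fmripower.** Correcting Table 2 does not by itself change 30 per group.

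**Conclusion.** The concern stands in a limited form. For attention, memory, executive function, impulsivity and BDI, the interactions in Table 2 represent AUD enlarging the net antiviral benefit, against the attenuation predicted in the hypotheses and in Expected outcomes. BDI conflicts on the raw changes as well, and so does impulsivity if lower means less impulsive. Cognition conflicts in the interaction only.

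The powers of 0.78 to 0.94 are correct for the effects entered but are not evidence of power to detect attenuation. Under the full-cancellation assumption they become 0.10 to 0.13 for cognition and impulsivity and 0.77 for BDI.

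The mismatch is not table-wide: the fatigue, MD, immune factor and T-cell interactions run in the predicted direction. A reader might also infer from the falling FA values that the FA interaction is reversed. It is not; only the sign of the HCV+ changes conflicts, and that is a separate point. Severity is moderate.

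**What to change.** 1. Reconcile the Table 2 group means for the five rows with the attenuation hypotheses, and restate the interaction power for each.
2. Where the predicted attenuation is below 0.91 SD, replace the general statement of sufficient power. Say instead that 30 per group detects an attenuating interaction of 0.91 SD or more with 80% power at the 0.10 level, and that smaller attenuation is not powered.
3. If larger gains with AUD are in fact expected for some outcomes, change the direction of the hypothesis for those outcomes before analysis.
4. State the direction of scoring for the BART/MID row.
5. Correct the sign of the FA changes in the two HCV+ groups, or explain it.

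The cost is protocol wording and a recalculated table. No participants, procedures, models or tests change. Some stated powers may become less favourable.
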